It is estimated that it will take 376 individuals in each of the comparison groups to ensure a statistical power of 80% and a type I error of 5%, considering an incidence of SARS-CoV-2 infection of 20% in BCG vaccinated, 30% in unvaccinated, 15% in covid-19 vaccinated. It is expected a reduction in the joint effect of BCG with the COVID-19 vaccine between 10% and 15% and that the percentage of people vaccinated with BCG in the cohort is 50% and the percentage of people vaccinated for Covid-19 in the cohort is 80%.

We will also use for the two outcomes (below) the sequential design the groups are followed up until there is a group with clear benefits or that both groups do not present difference. This design is used when the results need to be known very quickly. If there is a large difference between the treatments, then this study will be performed in a shorter time when compared to the parallel trial. The main ethical advantage is that if one treatment shows a superiority over the other, the study can already be stopped. However, the interim analyses will be previously planned, in such a way that the calculation of sample size allows the multiplicity of the tests. The meaning of p-values in sequential analyses also changes, because when using sequential analyses, more than one analysis is performed, and the typical definition of a p-value as data "at least as extreme" as observed needs to be reset. One solution is to sort the p-values of a series of sequential tests based on the downtime and at what time the test statistic was in a certain appearance, known as ordering.

OUTCOMES:

Primary Outcome

1. Compare the cumulative incidence of SARS-CoV-2 infection

It is estimated that it will take 376 individuals in each of the comparison groups to ensure a statistical power of 80% for the detection of a difference in effects of 10%, considering that the control group will have an accumulated incidence of SARS-CoV-2 infection of 30% after 6 months of follow-up, for a type I error of 5%.

2. Compare the cumulative incidence of severe forms of COVID-19

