We will also use for the two outcomes the sequential design the groups are followed up until there is a group with clear benefits or that both groups do not present difference. This design is used when the results need to be known very quickly. If there is a large difference between the treatments, then this study will be performed in a shorter time when compared to the parallel trial. The main ethical advantage is that if one treatment shows a superiority over the other, the study can already be stopped. However, the

interim analyses will be previously planned, in such a way that the calculation of sample size allows the multiplicity of the tests. The meaning of p-values in sequential analyses also changes, because when using sequential analyses, more than one analysis is performed, and the typical definition of a p-value as data "at least as extreme" as observed needs to be reset. One solution is to sort the p-values of a series of sequential tests based on the downtime and at what time the test statistic was in a certain appearance, known as ordering.

3. Assess the BCG vaccine-mediated immune response in healthcare professionals

SARS-CoV2 infection is estimated to occur in approximately 20% of health professionals vaccinated by BCG (experimental group), in 30% of health professionals not vaccinated by BCG (placebo group) and not vaccinated for COVID-19 and in 15% in COVID-19 vaccinated without BCG vaccine. A reduction of 10% to 15% of the joint effect of bcg vaccine with Covid-19 vaccine is expected.

In this scenario, with the bearing of 376 health professionals in each arm, if we assume that the percentage of covid-19 vaccinated is 80% and equal in each arm, SARS-CoV2 infection is expected to be detected in 15 professionals vaccinated only with BCG, in 23 professionals not vaccinated with BCG and COVID-19 vaccine, 45 professionals vaccinated for COVID-19 without bcg vaccine and 38 professionals vaccinated for COVID-19 and BCG. For each subgroup (vaccinated and not vaccinated with BCG) it will be possible to identify the predictive biomarkers of infection by comparing infected professionals with those who were not infected with SARS-CoV2.

INTERIM ANALYSIS PLAN:

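### The 80% power claimed at 376 per arm for SARS-CoV-2 infection does not fit the plan's own expected counts (68 vs 53 infections), which give about 32% two-sided or 44% one-sided

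*Combined protocol and SAP*

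**What the plan says.** The Sample size section of the Statistical Analysis Plan sets 376 per group for "a statistical power of 80% and a type I error of 5%, considering an incidence of SARS-CoV-2 infection of 20% in BCG vaccinated". It adds 30% in the unvaccinated and 15% in the COVID-19 vaccinated, and it assumes that "the percentage of people vaccinated for Covid-19 in the cohort is 80" per cent.

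Under OUTCOMES, Primary Outcome 1 repeats the claim: "It is estimated that it will take 376 individuals in each of the comparison groups to ensure a statistical power of 80" per cent for a 10% difference, "considering that the control group will have an accumulated incidence of SARS-CoV-2 infection of 30% after 6 months of follow-up".

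Primary Outcome 3 restates the rates more narrowly. Infection is expected "in 30% of health professionals not vaccinated by BCG (placebo group) and not vaccinated for COVID-19", and in 15% of those with the COVID-19 vaccine but not BCG. For people with both vaccines, "A reduction of 10% to 15% of the joint effect of bcg vaccine with Covid-19 vaccine is expected". The expected counts at 376 per arm then follow, "if we assume that the percentage of covid-19 vaccinated is 80% and equal in each arm": 15 infections with BCG only, 23 with neither vaccine, and "45 professionals vaccinated for COVID-19 without bcg vaccine and 38 professionals vaccinated for COVID-19 and BCG".

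**The concern.** Primary Outcome 1 treats 30% as the incidence of the whole control arm. It cannot be that if four in five control participants have a 15% risk and only the remaining fifth has a 30% risk. The planned 10-point difference has the same problem: it is the contrast within the COVID-19 unvaccinated fifth of the cohort, applied to the full arms.

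The claimed power belongs to the first primary outcome, which the plan compares between whole arms. If it is far too high for the scenario the plan itself expects, a non-significant result is the likeliest outcome even when BCG works as assumed. A reader relying on the stated 80% could then take that result as evidence against BCG.

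**Working it through.** **Inputs.** 376 per arm, 1:1 allocation, type I error 5% (Sample size; Intervention Plan). Incidences of 30%, 20% and 15%, and 80% COVID-19 vaccination (Sample size; Primary Outcome 3). Expected counts 23, 45, 15 and 38 (Primary Outcome 3). Sidedness is not stated, so both are shown. Losses and the interim look at Z = 2.78 are ignored.

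**Formula.** Pooled two-proportion test: power = Φ[(d − z·s0)/s1], plus the negligible opposite tail when two-sided. Here d = p1 − p2, s0 = √[2p̄(1 − p̄)/n], s1 = √[p1(1 − p1)/n + p2(1 − p2)/n], and z = 1.96 two-sided or 1.645 one-sided.

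**1. The plan's own figure.** For 30% vs 20%, 80% power needs 294 per arm two-sided (313 with continuity correction) or 231 one-sided (251). With 376 per arm, power is 88.8% two-sided and 93.7% one-sided. So the pair of 376 and 80% is not reproduced from the stated inputs, and the documents do not show how 376 was obtained.

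**2. Whole-arm incidence.** Each arm has 0.2 × 376 = 75.2 COVID-19 unvaccinated and 0.8 × 376 = 300.8 vaccinated participants.

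| Cell | Calculation | Expected | Printed |
|---|---|---|---|
| Placebo, unvaccinated | 75.2 × 0.30 | 22.6 | 23 |
| Placebo, vaccinated | 300.8 × 0.15 | 45.1 | 45 |
| BCG, unvaccinated | 75.2 × 0.20 | 15.0 | 15 |
| BCG, vaccinated | 300.8 × j | depends on j | 38 |

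Here j is the incidence with both vaccines. The printed totals are 68/376 = 18.1% on placebo and 53/376 = 14.1% on BCG. From the unrounded rates, placebo is 0.2 × 30% + 0.8 × 15% = 18.0%.

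**3. Power on the printed counts.** d = 0.0399, s0 = 0.0268, s1 = 0.0268.
- Two-sided: (0.0399 − 1.96 × 0.0268)/0.0268 ≈ −0.47, so power is 31.9%.
- One-sided: 43.8%.

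Simulation of 400,000 trials gives 32.0% and 43.8%. A test stratified by COVID-19 vaccination gives 32.2% and 44.2% on the printed counts; with the unvaccinated cells set at exactly 30% and 20% it gives 30.6% and 42.4%. Adjustment does not change the picture.

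**4. Sensitivity to the joint effect.** The scale of the 10% to 15% reduction is not defined. With placebo at 18.0% and BCG at 0.2 × 20% + 0.8 × j:

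| Reading | j | Infections with both vaccines | Power two-sided | Power one-sided |
|---|---|---|---|---|
| Any j that rounds to 38 | 12.47–12.80% | 37.5–38.5 | 29–33% | 40–44% |
| 10% relative reduction from 15% | 13.5% | 40.6 | 22.0% | 32.3% |
| 15% relative reduction from 15% | 12.75% | 38.4 | 29.4% | 41.0% |
| Incidence of 15% with both | 15% | 45.1 | 11.3% | 18.0% |
| Incidence of 10% with both | 10% | 30.1 | 63.5% | 74.6% |
| Absolute drop of 10 points | 5% | 15.0 | 98.4% | 99.3% |

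Of these readings only the absolute drop exceeds 80%, and it implies 15 infections where the plan prints 38.

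**5. What 376 per arm can detect.** From 18.0% on placebo, 80% power needs 10.8% on BCG two-sided (risk ratio 0.60, j ≈ 8.5%, about 26 infections with both vaccines) or 11.6% one-sided (risk ratio 0.64). For 18.1% vs 14.1%, 80% power would need 1,331 per arm two-sided or 1,048 one-sided.

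**6. If the expected counts occurred exactly.** Risk ratio = 53/68 = 0.78. SE(log RR) = √(1/53 − 1/376 + 1/68 − 1/376) = 0.168, so the 95% CI is 0.56 to 1.08. The pooled z is 1.49, two-sided p = 0.14.

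**The case against.** The counts are printed under the immune-response outcome, and Primary Outcome 1 claims 80% power for a 10-point difference, not for 4 points. Read alone, that sentence is conservative, since 376 per arm gives 88.8% for 30% vs 20%. But the Sample size paragraph attaches the same 376 and 80% to a cohort that is 80% vaccinated at 15% incidence. One trial population cannot have 30% control incidence for one outcome and 18% for another.

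The 32% does depend on rounded counts: 22.6 became 23, and 38 is compatible with a range of j. With unrounded rates and a 15% relative reduction, power is 29.4%. This is a fair qualification, and the defensible range on the printed counts is 29% to 33% two-sided.

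The allowance for multiple looks that the plan mentions might explain part of 376, but no such calculation is shown, and it would not repair the control rate. Finally, the plan will report risk ratios with 95% confidence intervals, and an interval of 0.56 to 1.08 would itself warn a careful reader. That softens the risk of misreading; it does not make the power statement correct.

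**Conclusion.** The concern holds. On the plan's own expected counts the whole-arm contrast is about 18% vs 14%, and power at 376 per arm is about 32% two-sided or 44% one-sided, not 80%. The figures assume a fixed-sample test at 5% without losses; losses would lower them. The conclusion does not depend on sidedness, on stratification by COVID-19 vaccination, or on any reading of the joint effect that comes near the printed 38 infections. This must be corrected, because it is the power statement of a primary outcome.

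**What to change.** In Sample size and Primary Outcome 1:

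1. Define the scale of the 10% to 15% joint reduction and the sidedness of the 5% test.
2. Replace 30% vs 20% with the whole-arm incidences implied by 80% COVID-19 vaccination: about 18% on placebo and 14% on BCG on the printed counts.
3. Replace 80% with the resulting power, about 32% two-sided on those counts, and show the method of calculation.
4. State the difference that 376 per arm detects with 80% power: about 18% vs 10.8%, risk ratio about 0.60, two-sided.

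If the sponsor intends another scale or sidedness, recalculate once and make the counts under Primary Outcome 3 agree.

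The change needs no extra participants and no new analysis. It does alter the stated power of a primary outcome, so it needs a protocol amendment and notification as the monitoring plan provides. The SCHEDULE lists an amendment submission to CEP/CONEP in August 2021, but the documents do not show whether this change could go with it. The drawback for the sponsor is a less favourable power statement.

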Regarding the effect of BCG vaccine administration on the cumulative incidence of SARS-CoV-2 infection or on severe forms of COVID-19, a single intermediate analysis will be performed when the number of volunteers included has reached half of the total sample scheduled to verify whether the evidence would already be conclusive and would allow the study to be interrupted. For type I error protection, intermediate analysis will use a Z value of 2.78 (Chow & Liu, 2004).

The analyses that will be performed in the intermediate analysis will be restricted to the following outcomes: accumulated incidence of SARS-CoV-2 infection, cumulative incidence of severe forms of COVID-19 and proportion of serious adverse events.

The following rules will be used to indicate early completion of the study after intermediate analysis:

- Significant difference in the effect of BCG judged by comparing the proportions of patients who develop SARS-CoV-2 infection or severe forms of COVID-19 in each arm of the study;

- If the effect of BCG is similar between groups and there is a significant difference in the cumulative proportion of serious adverse events;

The results will be evaluated by the Data and Safety Monitoring Committee, which will express the need to continue the study, based on the vaccine's performance in terms of the incidences of SARS-CoV-2 infection or severe forms of COVID-19 and adverse events.

Independent Data Monitoring and Security Committee:

The Data and Safety Monitoring Committee (CMDS) will be composed of three members not linked to participating institutions, in accordance with the Operational Guidelines for the Establishment and Functioning of Data Monitoring and Safety Committees of the Ministry of Health (2008).

This committee will be responsible for reviewing the protocol and progress of the study in all centers, with real-time meetings by videoconference, as detailed below, and will consist of:

[name] - Physician - Professor, Faculty of Medicine, Federal University of Rio Grande do Sul

[name] - Statistician - Institute of Collective Health Studies of the Federal University of Rio de Janeiro

[name] - Physician - Professor, Faculty of Medicine, Federal University of Minas Gerais

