An early safety assessment will be carried out when the first 100 participants (approximately 50 per arm) are included. Security data will be reviewed by a CMDS member or someone designated by a CMDS member. In addition, the Committee will review the progress of the study after the inclusion of every 100 additional participants through real-time meetings by videoconference.

CMDS activity plan:

Time of study	Activity	Form
---------------	----------	------

Before the start of the study	Protocol and MOP review	Real-time video conferencing scheduling
During the study	Early safety assessment after inclusion of the first 100 participants	Real-time video conferencing scheduling
	Evaluation of study progression per 100 participants included	Real-time video conferencing scheduling
	Adverse event analysis	Real-time video conferencing scheduling every 2 weeks
	Analysis of serious adverse events	Extraordinary meeting via real-time videoconferencing
	Intermediate analysis after the inclusion of 500 participants	Real-time video conferencing scheduling
At the close of the study	Evaluation of the conduct of the study and its results	Real-time video conferencing scheduling

Plan for monitoring and analysis of adverse events:

The definition for an adverse event described in the Manual for Notification of Adverse Events and Safety Monitoring in Clinical Trials (Anvisa, 2016) will be used as a definition for an adverse event: "any adverse medical occurrence in a patient or clinical trial participant to whom a pharmaceutical product has been administered and who does not necessarily have a causal relationship to treatment. As a result, an AE can be any unfavorable and unintentional sign, symptom, or disease (including results outside the reference range), associated with the use of a product under investigation, whether related to it or not. A serious AE shall be considered to have one resulting in any adverse experience with medicinal products, biological products or devices occurring at any dose and resulting in any of the following outcomes: a) death; b) threat to life; (c) persistent or significant disability/disability; d) requires hospitalization or prolongs hospitalization; e) congenital anomaly or birth defect; f) any suspected transmission of infectious agent by means of a drug or; g) clinically significant event."

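### The sequential-design text stops the trial for lack of difference without defining it, and the interim plan contains no such rule

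*Combined protocol and SAP*

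**What the plan says.** The sequential-design paragraph stands twice. In Sample size it says that "the groups are followed up until there is a group with clear benefits or that both groups do not present difference". Under OUTCOMES, Primary Outcome 2, it opens "We will also use for the two outcomes the sequential design the groups are followed up until there is a group with clear benefits" and continues in the same way. The paragraph gives no number, conditional power or minimum information for concluding that the groups do not differ. It adds that the interim analyses will be planned in advance.

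The INTERIM ANALYSIS PLAN says that "a single intermediate analysis will be performed when the number of volunteers included has reached half of the total sample scheduled" and sets one limit: "For type I error protection, intermediate analysis will use a Z value of 2.78". It then lists two rules for early completion:

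- "Significant difference in the effect of BCG judged by comparing the proportions of patients who develop SARS-CoV-2 infection or severe forms of COVID-19", compared between arms;
- "If the effect of BCG is similar between groups and there is a significant difference in the cumulative proportion of serious adverse events".

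On the decision itself it says: "The results will be evaluated by the Data and Safety Monitoring Committee, which will express the need to continue the study".

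The CMDS activity plan table gives a different time for the look: "Intermediate analysis after the inclusion of 500 participants".

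**The concern.** The design text names lack of difference as an end point of follow-up in its own right. The interim plan does not: similarity of effect matters there only when serious adverse events differ significantly. The interim plan does not say that it overrides the design text, and the design text does not say that it is background only. A committee holding this protocol could cite one section to stop and the other to continue.

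What is at stake is the meaning of an interim result that does not cross the boundary. At half the sample, such a result is likely even if BCG works as assumed. If it were taken as a showing of no difference, the trial could end with a negative conclusion that the data do not support. A limit chosen after the interim data are seen would not be prespecified.

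**Working it through.** **Inputs.** From Sample size and OUTCOMES: 376 per arm, 30% infected in control and 20% with BCG, 80% power, 5% type I error. From the INTERIM ANALYSIS PLAN: one look at half of 752, so 376 participants or 188 per arm, with Z = 2.78 (two-sided p = 0.0054). From the CMDS table: 500 participants, or 250 per arm. Assumptions: a two-sided test, complete 6-month outcomes at the look, and a final critical value of 1.979. No final value is stated; 1.979 is the value that keeps two-sided alpha at 5% with 2.78 at half information.

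**The plan's own figure.** For 30% versus 20%, 80% power and two-sided 5%, the pooled formula gives 294 per arm, or 313 with continuity correction, not 376. (313 × 1.20 = 375.6 would round up to 376, but the sample-size text states no inflation.) Power at 376 per arm is 88.8% for a single final test and 88.6% with the 2.78 look. The baseline below is therefore about 89%, not 80%. This mismatch does not decide the present point.

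**Interim at 188 per arm.**

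- Pooled standard error: √(2 × 0.25 × 0.75 / 188) = 0.04466.
- Expected Z: 0.10 / 0.04466 = 2.24, which is below 2.78.
- Unpooled standard error: √((0.30 × 0.70 + 0.20 × 0.80) / 188) = 0.04436.
- P(Z < 2.78) = Φ((2.78 × 0.04466 − 0.10) / 0.04436) = Φ(0.54) = 0.71.
- P(Z < 1.96) = Φ((1.96 × 0.04466 − 0.10) / 0.04436) = Φ(−0.28) = 0.39.
- P(Z < 0.5) = Φ((0.5 × 0.04466 − 0.10) / 0.04436) = Φ(−1.75) = 0.04.

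**Effect on power.** The table comes from a simulation of 2 million two-stage binomial trials with 30% versus 20% true. A trial succeeds if the interim Z exceeds 2.78, or if it continues and the final Z exceeds 1.979.

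| Lack of difference read as | Stopped, 188/arm | Power | Stopped, 250/arm | Power |
|---|---|---|---|---|
| Z < 2.78 | 70.6% | 29.4% | 57.8% | 42.2% |
| Z < 1.96 | 38.6% | 60.2% | 26.3% | 72.3% |
| Z < 1.645 | 27.3% | 70.3% | 17.1% | 79.9% |
| Z < 1.0 | 10.7% | 83.4% | 5.4% | 87.3% |
| Z < 0.5 | 4.2% | 87.2% | 1.7% | 88.4% |
| Z < 0 | 1.0% | 88.5% | 0.4% | 88.6% |
| no such stop | 0% | 88.6% | 0% | 88.6% |

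**Sensitivity.** The look is triggered by inclusion, not by completed follow-up. If only half of the cumulative incidence had accrued (15% versus 10%, an assumption), 91% of trials would fall below 2.78 and 69% below 1.96 at 188 per arm. No rate is given for severe forms, so the second outcome cannot be computed.

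**The case against.** A reader might infer that an effective BCG would often be abandoned at the interim and that the clause removes most of the power. The documents do not support that, for four reasons.

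- No section equates lack of difference with a non-significant interim Z. The sentence opens a general account of sequential designs, and the only ground for stopping which that account then names is superiority.
- The interim plan is the operative text. It describes the look as a check on whether the evidence is already conclusive. A non-significant result at half the sample is not conclusive.
- Reading the clause as Z below 2.78 defeats itself. Every trial would end at the interim, for benefit or for lack of it, and none could reach 752 participants. The 29% figure describes a design the documents do not contain.
- Stopping is not automatic. The monitoring committee advises on continuation, and the section on discontinuation for safety reasons requires ethics review before the study can be ended.

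It is also tempting to use the expected counts under OUTCOMES: 23 + 45 = 68 infections with placebo against 15 + 38 = 53 with BCG, each of 376. On these, 96% of trials fall below 2.78 and 82% below 1.96 at 188 per arm. But power at full size is then only about 31% with no such stop, so those failures mostly reflect the small assumed effect, not the clause.

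All of this stands against a claim of certain or frequent harm. It does not remove the contradiction. The paragraph is written as a commitment for this trial and appears twice, the interim plan does not disclaim it, and no limit is defined. If the interim plan governs, the clause is wrong and should go.

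**Conclusion.** The concern holds as an inconsistency between stopping rules, with an undefined criterion on one side. Its cost is conditional. If lack of difference means a non-significant interim at 188 per arm, 39% to 71% of trials of an effective BCG would stop, and power would fall from about 89% to 60% or 29%. At 250 per arm, 26% to 58% would stop. With a lenient limit such as Z below 0.5, about 4% would stop at 188 per arm and the loss is 88.6 − 87.2 = 1.4 points. These figures rest on 30% versus 20% being true, complete outcomes at the look, a two-sided test and a final critical value of about 1.98. The documents do not choose between the readings, and that is the defect.

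**What to change.** In Sample size and under OUTCOMES, delete the part of the sentence that ends follow-up when the groups do not differ. State that the rules in the INTERIM ANALYSIS PLAN alone govern early completion, so that recruitment continues to 752 if the interim boundary is not crossed and neither listed rule is met.

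If the sponsor wants a futility look, prespecify a non-binding numeric limit before the interim and report its effect on power under the design assumptions.

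At the same time, reconcile the timing of the look: half the sample (376) in the interim plan, 500 participants in the CMDS activity plan.

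The cost is a wording change, with no extra participants or data. It has to be made before the interim data are seen.

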The vaccine developed by the AstraZeneca/University of Oxford laboratory and produced in partnership with Fiocruz is a vaccine containing 5×10^{10} viral particles (pv) of the replication-deficient chimpanzee recombinant adenovirus vector (ChAdOx1), which expresses the Glycoprotein SARS-CoV-2 Spike (S). Produced in human embryonic brain cells (HEK) 293 genetically modified. After vaccination, in participants who were seronegative at the beginning of the study, seroconversion was demonstrated in $\geq 98\%$ of participants at 28 days after the first dose and $> 99\%$ at 28 days after the second. For prevention of illness by COVID-19 the vaccine demonstrated efficacy of 73% 22 days after the first dose (in a period of at least 3 months) and with strong indication of increased immune response when the second dose is provided within 3 months, which provides an increase of about 7.5 times in levels of humoral response (antibody production). Exploratory analyses showed that increased immunogenicity was associated with a longer dose interval and efficacy is currently more certainly demonstrated for intervals of 8 to 12 weeks. It is notepoint that there were no severe cases or deaths 21 days or more after vaccination, and 10 hospitalizations for severe COVID-19 were observed in the placebo group, including 1 death.

Allocation and randomization:

The randomization process will be carried out centrally and managed by the team of the Ribeirão Preto School of Medicine of USP (FMRP-USP), under the coordination of [name]. The process will be performed using the Microsoft Excel random number generation function®. The result will be composed of a randomization table with size appropriate to the N expected for the study (752 participants) and with a ratio of 1:1, which will be integrated to REDCap prior to the beginning of electronic data collection. The creation and validation of the table will be the responsibility of the data manager/project coordinator.

By including a participant in the study, REDCap will consult the existing randomization table and excel® sequentially to allocated it to one of the groups defined in the study. It is noteworthy that REDCap does not, on its own, perform any form of randomization, which will be based exclusively on the said table in Excel®.

Study visits:

Social networks and electronic media will be used to disseminate the study through folders and calls about the research.

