According to CNS Resolution No. 441 of 2011 (Art. 1) and Ordinance MS No. 2,201 of 2011 (Art. 3), any organized collection of human biological material collected for scientific research purposes, including samples intended for routine examinations in a clinical trial (e.g., blood count and renal function) are considered as constituents of a biorepository or biobank. The biological material will be used as provided for in the research protocol, with no further future analyses different from those foreseen. If there is a proposal for future use of the stored samples, approval in the CEP/CONEP system will be required and a new protocol and TCLE will be submitted so that each participant can choose whether or not to allow the use of the samples for future studies.

Statistical Analysis Plan:

The primary efficacy analysis will compare the cumulative incidence of SARS-CoV-2 infection and the cumulative incidence of severe forms of COVID-19.

These analyses will occur when the last enrolled research subject has completed 30 days and 6 months of preventive treatment and will be performed using the results of COVID-19 diagnostic tests, as well as the data available in participating hospitals and national electronic notification systems of COVID-19. A modified treatment intention analysis (MITT) and protocol (PP) will be performed. The safety and tolerability analysis will consist of all patients who have been randomized and received a dose of the vaccine or placebo. Based on serum immune response concentrations, we will calculate certain immunoinflammatory variables related to the use of BCG versus placebo among subjects infected and not infected by COVID-19 among the categories with COVID-19 vaccine (Coronavac® or Covishield®) and without covid-19 vaccine.

The intervention and control groups will be compared at the time of inclusion in the study in relation to sociodemographic, clinical, radiological and biochemical imaging variables, in order to evaluate the adequacy of the randomization process. Multivariate

analyses using logistic regression or Poisson models with robust variance will be used to evaluate the effect of BCG vaccine on primary and secondary outcomes. Associations will be expressed in the form of risk ratios and respective 95% confidence intervals. Data imputation may be required and the *random forest system* will be used. Statistical software R, version 10.0.

Sample size:

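### The single interim has two triggers (376 and 500), and the plan gives no final critical value and no rule for sharing the error between infection and severe COVID-19

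*Combined protocol and SAP*

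**What the plan says.** - **Trigger.** The Interim Analysis Plan sets one interim "when the number of volunteers included has reached half of the total sample scheduled". Allocation and randomization describes a table of "size appropriate to the N expected for the study (752 participants", so half is 376. The CMDS activity plan lists "Intermediate analysis after the inclusion of 500 participants".
- **Critical value.** The Interim Analysis Plan says the "intermediate analysis will use a Z value of 2.78", citing a textbook. No value for the final analysis appears.
- **Outcomes.** One ground for early completion is a significant difference found by "comparing the proportions of patients who develop SARS-CoV-2 infection or severe forms of COVID-19 in each arm of the study". The Statistical Analysis Plan makes both outcomes primary.
- **Times.** "These analyses will occur when the last enrolled research subject has completed 30 days and 6 months of preventive treatment". It does not say whether the 30 days is an earlier data cut-off or a separate 30-day outcome.
- **Error rate.** Under Primary Outcome 1, 376 per group gives 80% power for a 10-point difference, with a control-group "accumulated incidence of SARS-CoV-2 infection of 30% after 6 months of follow-up, for a type I error of 5" per cent. The Sample size section repeats the 5% alongside infection rates.
- **Multiplicity.** Interim analyses are to be planned "in such a way that the calculation of sample size allows the multiplicity of the tests". Ordering of p-values is described as one possible solution and is not adopted. No alpha split, testing order or spending function is given.

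**The concern.** An interim boundary protects the error rate only when it is paired with a final value, and the pair depends on how much information is available at the interim. Here the interim has two possible positions and no paired value. The rule also accepts either of two primary outcomes, at two analysis times, without saying how they share the error. Two analysts could run the interim at different points, use different final thresholds and claim success on different outcomes, each consistent with the text. Such choices are not credible once unblinded results have been seen.

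**Working it through.** **Assumptions.** Tests are two-sided (the plan does not say). The final value is taken as 1.96 where stated. No rate of severe COVID-19 is given, so ranges are shown. Only infection and severe COVID-19 are counted, not the immune-response outcome.

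**1. The plan's own sample size.** With p1 = 0.30, p2 = 0.20 and mean 0.25:

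n = [z(1−α/2)·√(2·0.25·0.75) + 0.8416·√(0.21 + 0.16)]² / 0.10²

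- α = 5%: (1.960 × 0.6124 + 0.8416 × 0.6083)² / 0.01 = 293.2, so 294 per group, or 313 with continuity correction. The stated 376 is not reproduced.
- α = 2.5%: z = 2.241 gives 356, or 375 with continuity correction.
- A 20% inflation of 313: 313 × 1.2 = 375.6, which rounds up to 376.

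The text states neither of the last two routes, so 376 neither confirms nor excludes an alpha split.

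**2. The trigger.** 752 / 2 = 376 (50%); 500 / 752 = 66.5%. The value 2.78 does not identify which is meant. It lies near the O'Brien-Fleming bound for 5% at 50% information (2.797) and also near the bound for 2.5% at 66.5% (2.786).

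**3. One outcome, one interim.** α = 1 − P(|Z1| < 2.78 and |Z2| < c), with correlation √t between Z1 and Z2.

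| Information t | α with c = 1.96 | c for 5% | c for 2.5% |
|---|---|---|---|
| 0.50 | 5.21% | 1.979 | 2.291 |
| 0.665 | 5.10% | 1.969 | 2.272 |

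At information as low as 8% the error is still only 5.5%. The trigger conflict therefore has little effect on the error.

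**4. Two outcomes, chance of at least one false positive in either direction.**

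- Independent, c = 1.96: 1 − (1 − 0.0521)² = 10.2% at t = 0.50; 1 − (1 − 0.0510)² = 9.9% at 0.665.
- Correlated, t = 0.50: 9.4% at correlation 0.5, 8.9% at 0.67, 8.2% at 0.8 (8.0% at 0.8 with t = 0.665).
- Severe events at 0.3%, in a participant-level simulation with severe cases nested in infections: 7.0%.
- Independent, with the paired 1.979 for both outcomes: 9.7%. A paired value in the cited textbook would not close this gap unless the two outcomes are also ordered or split.
- Independent, with 2.291 for both: 4.9%.

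**5. Adding the 30-day analysis, also tested at 1.96.** As an earlier cut-off of the same data, the two-outcome figure becomes roughly 11–15%; as a separate 30-day outcome, roughly 14–18%. With severe events at 0.3%, the figures are 8.9% and about 11%.

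**6. What inclusions measure.** The Schedule allows 427 days of recruitment (30/10/2020 to 31/12/2021). Under uniform accrual, 376 are included at 0.5 × 427 = day 213.5, when 752 × (213.5 − 180) / 427 = 59 have completed 180 days. At 500 (day 283.9) the number is 183. Under the 4-month recruitment mentioned in the Intervention section it is zero at either trigger. An inclusion count therefore does not fix the information on a 6-month outcome.

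**The case against.** A reader might infer that the plan, followed as written, doubles its stated 5%. The documents do not support that, for three reasons. First, 1.96 at the end is an assumption: no final value is printed, and the page cited for 2.78 may supply one that cannot be seen here. Second, the 5% is an input to the infection sizing and is nowhere attached to the set of primary outcomes; for infection alone, with one final analysis, it is nearly met. Third, the two-outcome figures count false findings of harm as well as benefit, and false benefit claims are about half of them.

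Two other readings also go too far. The conflict between 376 and 500 is not a source of material error inflation. The closeness of 375 to 376 is not evidence of a built-in 2.5% split, because an ordinary 20% inflation reaches 376 as well.

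It can also be said that this is a phase II-B trial, that the committee only advises, and that any stop needs ethics review first. That limits the consequence of the interim, but most of the error arises at the final tests, which those safeguards do not touch.

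What survives is narrower. The trigger conflict is real, the final value is absent, and an either-or rule with no order or split does not control the error across two outcomes merely because each is tested near 5%.

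**Conclusion.** The point holds as a gap and a contradiction that should be fixed, not as a demonstrated breach of 5%. The two statements of when the interim occurs are incompatible, and the decision rule is incomplete. On two-sided tests with an assumed final 1.96, the chance of at least one false positive across infection and severe COVID-19 is about 8–10%, depending on their correlation, and about 7% if severe cases are very rare. It is higher if the 30-day analysis is also tested. Whether the sample size allows for any of this cannot be determined from the text.

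**What to change.** 1. Reconcile the Interim Analysis Plan and the CMDS activity plan to one trigger, and compute the boundary at the information actually available then. A trigger based on the number of infections is an option, not a necessity.
2. State the final value paired with 2.78: for 5% on one outcome, 1.979 at 50% information or 1.969 at 66.5%.
3. State how the two outcomes share the 5%, by one of two routes:
   - Fixed order, infection first and severe COVID-19 only if infection is significant, applied at the interim as well. The cost is that a difference in severe COVID-19 alone could no longer indicate early completion for efficacy, a ground the present rule grants.
   - A 2.5% split, with final value 2.291 (50%) or 2.272 (66.5%). The cost is power for infection: with the interim, 81.5% against 88.5% under the fixed order for 30% versus 20%. For the counts expected under Primary Outcome 3 (23 + 45 = 68 versus 15 + 38 = 53 of 376 each), it is 21.8% against 31.5%.
4. Name the 6-month analysis, on which the infection sizing rests, as confirmatory. Say whether 30 days is a cut-off or an outcome horizon, and treat it as descriptive.
5. State how 376 per group was obtained, including any allowance for multiplicity or dropout.

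These are text changes, but timing matters. Under uniform accrual over the Schedule's dates, 376 would be included around the end of May 2021, before the amendment submission listed for August 2021. If the interim has already been run, the plan should record when it was run and on how much information, and the final value should be derived from that without reference to the unblinded results.
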